9.1 Primary Endpoint

9.1.1 Time to Death Through Day 90 After Randomization

Time to 90-day overall survival will be calculated as the earlier of [(date of death) – randomization date] for those subjects who died without having liver transplant on or prior 90 days. Subjects who did not die, or had a liver transplant before death will have their time to event censored at the earlier of the following times:

- Date of last contact.
- Liver transplant date
- Cut-off date (i.e. 90 days) for analysis

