3.1 Efficacy Objectives

3.1.1 Primary Efficacy Objective

- To evaluate the effect of SMT+PE-A 5% on 90-day overall survival.

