5.3.2 Discontinuation of Subjects from Treatment

If a subject receives a liver transplant, study treatment and all treatment related assessments will be discontinued upon transplant. The criteria to determine when a subject becomes a candidate for liver transplantation is described in [Section 5.3.2.1](#). The subject will continue to have Days 21, 28, 60, and 90 follow-up procedures performed.

Adverse events that will determine a subject’s discontinuation from study treatment include the following:

- New septic shock with norepinephrine requirements >0.5 mcg/kg/min
- Severe bleeding (gastrointestinal or other)
 - Any intracranial bleeding (excluding microhemorrhages <10 mm evident only on gradient-echo MRI)
 - Clinically overt signs of hemorrhage associated with a drop in hemoglobin of ≥5 g/dL, or a ≥15% absolute decrease in hematocrit, or requirement of ≥4 U of blood
 - Fatal bleeding (bleeding that directly results in death within 7 days)
- Anaphylactic shock or severe transfusion-related acute lung injury (TRALI) defined as new acute lung injury (ALI)/ARDS characterized by sudden development of dyspnea, bilateral infiltrates in chest X-ray, moderate or severe hypoxemia (PaO2/FiO2 < 200) with or without hypotension, and fever that develop during or within six hours after blood product administration
- Any other severe AEs (ie, acute myocardial infarction, cerebral hemorrhage, or intestinal necrosis) that preclude the continuation of the subject in the trial

Subjects with any one of these severe AEs will be discontinued from study treatment and all treatment-related assessments, and should continue to have subsequent planned visit assessment procedures performed.

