7.1.1 Primary Efficacy Variable

- The primary efficacy variable will be time to death through Day 90 after randomization of SMT+PE-A 5% versus SMT alone.

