9.2.2 Time to Death Through 28-Day After Randomization

Time to 28-day overall survival will be calculated as [date of death – randomization date] for those subjects who died without having liver transplant on or prior to 28 days. Subjects who did not die or had a liver transplant before death, will have their time to event censored at the earlier of the following times:

- Date of last contact.
- Liver transplant date
- Cut-off date (i.e. 28 days) for analysis

This endpoint will be analyzed in the same way as outlined in section 9.1.2 for the primary analysis. The probability of event-free survival for the endpoint at day 28 for the endpoint and 95% confidence interval (CI) will be estimated.

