9.2.3 Secondary Efficacy Sensitivity Analyses

A sensitivity analysis will be conducted on the ITT populations to evaluate time to 28-day transplant-free survival, without treating liver transplant as a censoring event. For subjects who do not die, will have their time to event will be censored at the earlier of the following:

- Date of last contact.
- Cut-off date (i.e. 28 days) for analysis

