10.5 Physical Assessment

Physical assessment findings (normal and abnormal) will be listed for each subject and summarized by treatment and visit. Any clinically significant abnormality, as determined by the investigator, experienced by a subject during the clinical study and not already present at baseline will be reported as an AE.

11 Interim Analysis

No interim analysis is planned.

12 Changes in Planned Analysis

Changes in the analysis of longitudinal outcomes

The MMRM will be used to analyze the longitudinal continuous outcomes [e.g., CLIF-C OF score, CLIF-C ACLF score, MELD score, Child-Pugh score and Systemic inflammation assessment], and a general linear model implemented in SAS Proc GENMOD will be used to analyze the longitudinal binary or ordinal outcomes [Child-Pugh Sub-Score, CLIF-C OF Sub-Score]. However, protocol section 9.1.2.4 stated that exploratory endpoints would be analyzed by means of analysis of covariance (ANCOVA); this method is not suitable for longitudinal outcomes with missing data.

Adding Ascites Assessment as an exploratory endpoint

Although not included as an exploratory objective in the protocol an Ascites assessment is performed at each visit. The Ascites assessments will be summarized by visit and presented as an exploratory efficacy endpoint. This has been added for completeness.

Exploratory Endpoints

The protocol states the analyses of the primary and secondary efficacy endpoints and exploratory time to event endpoints will be repeated for each sub-group of subjects with ACLF-1b, ACLF-2, or ACLF-3a for exploratory purposes. *Additional subgroup analyses by age group, sex, race, and region (EU versus NA) may be performed for the primary endpoint.* Region was pre-specified as the only additional sub-group analysis on the primary endpoint and this sub-group analyses will also be performed on the secondary and exploratory time-to-event endpoints. This additional by region sub-group analyses is performed to determine if there are treatment effect differences in regions.

Adding a sensitivity analysis in which liver transplant is not a censoring event for the endpoints

A sensitivity analysis will be added to not consider liver transplant as a censoring event in time to death endpoints. This analysis is incorporated in the appropriate sections above (see section [9.1.3](#), [9.2.3](#))

Adding additional categories in treatment emergent adverse event (TEAE)

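### SAP 9.1.1 and 9.2.2 call their endpoints overall survival but censor at liver transplant, leaving the protocol's all-death endpoint to a sensitivity analysis

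*SAP*

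**What the plan says.** Protocol 3.1.1 sets the primary objective: "To evaluate the effect of SMT+PE-A 5% on 90-day overall survival". Protocol 7.1.1 defines the variable: "The primary efficacy variable will be time to death through Day 90 after randomization of SMT+PE-A 5% versus SMT alone". Protocol 9.7 applies it to everyone randomized. The protocol has no rule that censors at transplant. Protocol 5.3.2 stops study treatment at transplant but keeps the subject under observation: "The subject will continue to have Days 21, 28, 60, and 90 follow-up procedures performed". Transplant, survival and cause of death are recorded at Days 28 and 90 (Protocol 7.2.1.3.2). Transplant-free survival is a separate secondary endpoint (7.1.2).

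SAP 9.1.1 counts a death only if no transplant came before it. Survivors and those who "had a liver transplant before death will have their time to event censored at the earlier of the following times"; the listed times are last contact, transplant and Day 90. SAP 9.1.2 declares superiority on this endpoint. SAP 9.2.2 counts 28-day deaths only "for those subjects who died without having liver transplant on or prior to 28 days" and censors at transplant in the same way.

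SAP 9.1.3 adds a 90-day analysis, on ITT and PP, that does not censor at transplant. SAP 9.2.3 adds the Day 28 counterpart but calls it "time to 28-day transplant-free survival, without treating liver transplant as a censoring event". Section 12 has an entry headed "Adding a sensitivity analysis in which liver transplant is not a censoring event for the endpoints". It has no entry saying that the primary analysis censors at transplant.

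**The concern.** Overall survival ordinarily counts every death. Once transplant censors, the primary hazard ratio describes death in a setting where nobody is transplanted. It does so without bias only if transplanted subjects would otherwise have had the same prognosis as similar subjects still at risk.

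That assumption is doubtful. Protocol 5.3.2.1 ties transplant evaluation to MELD, Child-Pugh, worsening renal function and rapid decompensation, and leaves the decision to individual judgement. All of these also track the risk of death. The trial is open-label (Protocol 4.3.3), so the decision is made with the arm known. Treatment could lower transplant use by improving the scores, or raise it by keeping subjects fit for surgery; the documents do not say which to expect.

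The first secondary endpoint (SAP 9.2.1) also ends at transplant, where transplant is itself the event. So no test in the fixed sequence of SAP 6.5 counts a death after transplant, although the data to count it are collected.

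**Working it through.** **1. The plan's own figures.** Inputs from Protocol 9.2: 50% against 35% mortality at Day 90, two-sided 5%, 80% power. The hazard ratio is ln(0.65)/ln(0.50) = 0.6215. The Schoenfeld formula gives 139 events and the Freedman formula 145, which bracket the stated 141. Mean mortality is (0.50 + 0.35)/2 = 0.425, so 141/0.425 = 331.8, or 332 subjects; 332/0.9 = 369, stated as 370. The calculation takes all subjects as followed for 90 days, with no transplant censoring.

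**2. How many transplants.** No rate is given for this trial. Protocol 2.7 says that fewer than half of ACLF patients are listed and that transplant is feasible in 10–25% of those. This gives at most 0.5 × 0.10 = 5% to 0.5 × 0.25 = 12.5%. These are background figures without a 90-day window, so the range is an inference.

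**3. Simulation A: severity drives both death and transplant.** There are 380 × 0.9 = 342 evaluable subjects and 50% control mortality, as in the plan. Assumed: log-normal frailty (SD 1) on the death and transplant hazards, a conditional treatment hazard ratio of 0.5, and 19% mortality in the 90 days after transplant. The 19% is 100% minus the 81% long-term survival in Protocol 2.7, so it is borrowed and is not a 90-day figure.

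**4. Simulation B: 200,000 subjects per arm.** Assumed: gamma frailty with mean and variance 1, a death hazard of 1/90 per day times the frailty (50% control mortality without transplant), 10% mortality in the 90 days after transplant, and a transplant hazard of 0.002 or 0.004 per day. The transplant hazard is either unrelated to frailty or proportional to it.

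| Simulation | Treatment effect on death before transplant | Transplanted, SMT / SMT+PE-A | HR, all deaths | HR, censored at transplant |
|---|---|---|---|---|
| A | yes | 12.5% / 12.5% | 0.588 | 0.570 |
| A | yes | 25% / 25% (assumed upper bound) | 0.599 | 0.558 |
| A | yes | 12.5% / 5% | 0.629 | 0.599 |
| B, unrelated to frailty | yes (0.6) | 11.4% / 13.0% | 0.675 | 0.669 |
| B, unrelated to frailty | none | 21.4% / 11.6% | 1.072 | 1.007 |
| B, unrelated to frailty | none | 11.5% / 21.2% | 0.947 | 1.007 |
| B, driven by frailty | none | 15.2% / 8.2% | 1.093 | 1.046 |
| B, driven by frailty | none | 8.3% / 15.1% | 0.917 | 0.957 |

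In A at 12.5%, control mortality by Kaplan-Meier is 47.7% censored against 45.5% counting all deaths. Deaths left out of the primary analysis are 129.7 − 124.7 = 5.0 per trial. At 25% they are 118.7 − 108.1 = 10.6. Repeating A gave 0.568 against 0.587 at 12.5%, and 0.565 against 0.608 at 25%.

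**5. Reading.** With equal rates inside the inferred range the two hazard ratios nearly agree: 0.570/0.588 = 0.97. With unequal rates they separate, in a direction set by which arm has more transplants. In the last two rows the censored ratio itself moves off 1 although treatment does nothing to death before transplant. That is informative censoring. In all four no-effect rows at least one arm's transplant rate is above 12.5%.

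**The case against.** The strongest reply is that the protocol's endpoint is already in the plan. SAP 9.1.3 analyses it on ITT and PP, and 9.2.3 does so for Day 28. A reader might infer that post-transplant deaths are never counted or are thrown away. The documents do not support that: those deaths are left out of the decision-making analysis and included in the sensitivity analyses. What remains is that 9.1.2 declares superiority on the censored endpoint alone, and a sensitivity analysis does not change that decision.

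A second reply is that the protocol defers data handling, including missing data, to the SAP (Protocol 9.1, 9.5). But survival after transplant is not missing. It is scheduled to be collected, so the rule changes the endpoint and does not fill a gap.

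A third reply is that the effect is small. For equal transplant rates within 5–12.5%, this stands.

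Three further inferences also go too far:

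- **Benefit is overstated.** The table shows gaps in both directions.
- **The 141-event requirement is breached because of censoring.** The adopted 380 came from the chi-square calculation. In simulation A at 12.5%, counting all deaths already gives only 129.7 events. SAP Section 2 also says that the trial ended early, so planned event counts no longer apply. If transplant is unrelated to risk and equal by arm, the power cost is modest: 342 × 0.425 = 145 deaths (81.8%) with no transplants, against about 141 (80.6%) with 5% and 137 (79.4%) with 10%.
- **The censoring rule was introduced after follow-up ended.** The version history shows that the non-censoring sensitivity analysis was added in version 2.0. It does not show how version 1.0 treated transplant.

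**Conclusion.** The point holds. The analysis that decides superiority, and the 28-day secondary, measure death without prior transplant under the name overall survival. The endpoint the protocol defines is left to a sensitivity analysis, and Section 12 does not declare the departure. This follows from the text alone and needs no simulation.

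The numerical consequence is uncertain. It is small when arms have equal, low transplant rates (0.57 against 0.59 at 12.5%). It can go either way when rates differ (1.01 censored against 1.07 or 0.95 at about 21% against 12%). These figures rest on assumed transplant rates, frailty models and post-transplant mortality of 19% or 10%, none of which the documents give for this trial. That the censoring is informative is plausible from Protocol 5.3.2.1 and the open-label design, but it is not shown.

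**What to change.** - In SAP 9.1.1 and 9.2.2, count every death from randomization through Day 90 (Day 28), before or after transplant, and censor only at last contact or the cut-off.
- Move the transplant-censored versions to 9.1.3 and 9.2.3 as sensitivity analyses. Keep transplant-or-death as the first secondary endpoint.
- Report the number and timing of transplants by arm, so that any gap between the two analyses can be interpreted.
- Correct the label in 9.2.3. Transplant is neither an event nor a censoring time there, so the analysis is 28-day overall survival; transplant-free survival at Day 28 is the exploratory endpoint of 9.3.1.3.
- Record the change in Section 12 with Protocol 3.1.1, 7.1.1 and 5.3.2 as its basis.

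Both 90-day derivations and both 28-day derivations are already specified, and no new data are needed. The cost is in documentation. The last patient visit was 14 April 2025 and SAP version 3.0 is dated 15 October 2025, in an open-label trial. Section 12 should therefore say plainly that the change came after the last visit, that it restores the protocol's endpoint, and what was known of the outcome data when it was made.

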9.1.2 Primary Analysis

The analysis of the primary endpoint will be performed for the ITT population.

The objective of this study is to demonstrate superiority of SMT + PE-A 5% over SMT alone with regards to 90-day overall survival after study randomization. The null hypothesis is that the hazard functions for death are the same for the 2 treatment groups, or equivalently, the hazard ratio is equal to 1. The alternative hypothesis is that the hazard functions for death are not the same for the 2 treatment groups, or equivalently, the hazard ratio is not equal to 1.

Instituto Grifols, S.A. / Protocol IG1407

Null Hypothesis H_0 : HR (SMT + PE-A 5% / SMT alone) = 1

Alternate Hypothesis H_a : HR (SMT + PE-A 5% / SMT alone) \neq 1

The Hazard ratio and 95% CIs will be estimated using a stratified Cox Proportional-Hazards (PH) model, where the stratification factors include the region (Europe or North America) and 3 ACLF grades (ACLF-1b, ACLF-2, or ACLF-3a) used in the randomization and recorded in IWRS.

Superiority will be demonstrated if the p-value of the estimate of the treatment effect from the PH model for SMT + PE-A 5% compared to the SMT alone group is less than or equal to 0.05 and the hazard ratio is less than 1.

The 90-day survival will be summarized by means of Kaplan-Meier survival estimates and curves. The number and percentage of subjects with events of death and subjects without events (censored) will be presented by treatment. The median, 25th percentile and 75th percentile for survival in days will be calculated by treatment using Kaplan-Meier estimates, and the 95% confidence intervals (CI) for the median of each treatment group will be calculated using the Brookmeyer-Crowley method. The probability of survival for the endpoint at day 28, and 90 for the endpoint and 95% CI will be estimated using the Kaplan-Meier product limit method and Greenwood's formula for standard error. The survival functions will be compared between treatment groups using a log-rank test stratified by region (Europe or North America) and 3 ACLF grades (ACLF-1b, ACLF-2 or ACLF-3a) as recorded in IWRS.

9.1.3 Sensitivity Analyses

The primary analysis outlined in [9.1.2](#) will be repeated using the per-protocol population as a sensitivity analysis.

An unstratified analysis of 90-day overall survival will be performed as a sensitivity analysis on the ITT population and PP population, respectively.

A sensitivity analysis will be conducted on both the ITT and PP populations to evaluate time to 90-day overall survival, without treating liver transplant as a censoring event. For subjects who do not die, their time to event will be censored at the earlier of the following:

- Date of last contact.
- Cut-off date (i.e. 90days) for analysis

A sensitivity analysis will be used to assess whether the magnitude of treatment effect (i.e., hazard ratio) is consistent between 3 ACLF subgroups (ACLF-1b, ACLF-2 and ACLF-3a) by a stratified Cox model, where the stratification factors include the region (Europe or North America) as recorded in IWRS only, ACLF status and treatment will be included as fixed effects, and treatment by ACLF status interaction. This will be performed on the ITT population

If the IWRS stratification factors region (Europe or North America) and ACLF grade (ACLF-1b, ACLF-2 and ACLF-3a) do not match with the corresponding information collected on the eCRF for more than 3% of subjects, the primary analysis will be repeated adjusting for the stratification variables as recorded on the eCRF. This will be performed on the ITT population only.

The primary analysis will be repeated as a sensitivity analysis censoring a subject at their last contact date if a subject is missing a death date in the vital status eCRF page, but death is recorded as the reason for early termination on the end of study/early termination eCRF page. This will be performed on the ITT population only.

9.2 Secondary Endpoints

The analysis of the secondary endpoints will be performed for the ITT population using the same methodology as the primary analysis for the primary endpoint described in section 9.1.2. fixed-sequence testing method will be used for the analysis of secondary endpoints, as described in section 6.5 above. The secondary endpoint definitions are presented in the order in which testing will be performed.

9.2.1 Time to Liver Transplantation or Death Through 90-Day After Randomization

Time to 90-day liver transplant free survival will be calculated as [the earlier of the date of liver transplantation or date of death – randomization date for those subjects who died or had a liver transplant on or prior to 90 days. Subjects who neither died nor had a liver transplant, will have their time to event censored at the earlier of the following times:

- Date of last contact.
- Cut-off date(i.e. 90 days) for analysis.

This endpoint will be analyzed in the same way as outlined in section 9.1.2 for the primary analysis.

9.2.2 Time to Death Through 28-Day After Randomization

Time to 28-day overall survival will be calculated as [date of death – randomization date] for those subjects who died without having liver transplant on or prior to 28 days. Subjects who did not die or had a liver transplant before death, will have their time to event censored at the earlier of the following times:

- Date of last contact.
- Liver transplant date
- Cut-off date (i.e. 28 days) for analysis

This endpoint will be analyzed in the same way as outlined in section 9.1.2 for the primary analysis. The probability of event-free survival for the endpoint at day 28 for the endpoint and 95% confidence interval (CI) will be estimated.

9.2.3 Secondary Efficacy Sensitivity Analyses

A sensitivity analysis will be conducted on the ITT populations to evaluate time to 28-day transplant-free survival, without treating liver transplant as a censoring event. For subjects who do not die, will have their time to event will be censored at the earlier of the following:

- Date of last contact.
- Cut-off date (i.e. 28 days) for analysis

9.3 Exploratory Endpoints

The analysis of the exploratory endpoints will be performed for the ITT population.

9.3.1 Exploratory Time to Event Endpoints after Randomization

The following endpoints will be analyzed using the same methodology as the primary analysis for the primary endpoint described in section 9.1.2.

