The number and percentage of subjects showing a specific ACLF course (resolution, improvement, steady course, or worsening) or a specific organ failure as well as the number and percentage of new infections at the end of hospitalization will be compared between treatment groups by means of Fisher’s exact or Chi-square test. As sensitivity analyses, treatment effects will be adjusted for clinically and statistically significant imbalances in baseline characteristics by fitting appropriate Logistic Regression model or by means of the Cochran-Mantel-Haenszel (CMH) test.

Time-to-hospital discharge will be estimated by the Kaplan-Meier method and compared between treatment groups by the Log-rank test stratified by region and the 3 ACLF grades.

Albumin level in serum will listed for each subject and summarized by treatment group.

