6.5 Hypothesis Testing and Multiplicity Adjustments

All statistical tests will be two-sided with significance level fixed at 0.05.

The fixed-sequence testing method will be used to adjust for multiplicity in the analyses of the secondary efficacy endpoints (using ITT population). Specifically, the superiority of SMT+PE-A 5% versus SMT alone for the secondary efficacy endpoints will only be tested if the superiority for the primary efficacy endpoint is demonstrated at the two-sided significance level of 5% (using ITT population).

Instituto Grifols, S.A. / Protocol IG1407

For the secondary efficacy endpoints, each subsequent hypothesis is tested only if the superiority for the previous comparison(s) has been demonstrated at a two-sided significance level of 5%. The order in which the null hypotheses will be tested is predetermined for the secondary efficacy endpoints as follows:

1. Time to transplant or death through Day 90 after randomization of SMT+PE-A 5% versus SMT alone
2. Time to death through Day 28 after randomization SMT+PE-A 5% versus SMT alone

No other adjustments for multiplicity are planned. P-values will be displayed for all the above pre-specified tests for completeness; interpretation and reporting of significant hypothesis test results will follow the fixed sequence approach described.

7 Subject Disposition and Demographics

Unless otherwise noted, all demographics listings and summaries will be based on the ITT population.

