9.3.1.4 Time to hospital discharge

Time to hospital discharge will be calculated as [discharge date -randomization date). Subjects who had a liver transplant or death during the hospitalization will be censored to the earliest date of liver transplant or death. Subjects who haven't been discharged before the end of study and have not had a liver transplant or death will be censored to their last contact date. The endpoint will be analyzed in ITT population.

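### Time to hospital discharge inherits a hazard-ratio-below-1 superiority criterion that points the wrong way for a favourable event, and its Kaplan-Meier estimates overstate discharge because in-hospital deaths and transplants are censored

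*SAP*

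**What the plan says.** SAP 9.3.1 opens four exploratory endpoints with one cross-reference: "The following endpoints will be analyzed using the same methodology as the primary analysis for the primary endpoint described in section 9.1.2". The four are in-hospital death (9.3.1.1), in-hospital transplant or death (9.3.1.2), transplant or death to Day 28 (9.3.1.3) and time to hospital discharge (9.3.1.4).

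SAP 9.1.2 sets the null hypothesis as "HR (SMT + PE-A 5% / SMT alone) = 1", so the treated arm is the numerator. Superiority requires that the p-value "is less than or equal to 0.05 and the hazard ratio is less than 1". The same section asks for a stratified Cox model, a stratified log-rank test, Kaplan-Meier quartiles, and Kaplan-Meier probabilities at Days 28 and 90.

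For discharge, SAP 9.3.1.4 defines the time as follows: "Time to hospital discharge will be calculated as [discharge date -randomization date". On censoring it says: "Subjects who had a liver transplant or death during the hospitalization will be censored to the earliest date of liver transplant or death".

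Protocol 9.1.2.4 plans less for this endpoint: "Time-to-hospital discharge will be estimated by the Kaplan-Meier method and compared between treatment groups by the Log-rank test stratified by region" and ACLF grade. It sets no hazard-ratio criterion.

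**The concern.** There are two separate defects.

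**Direction.** For 9.3.1.1 to 9.3.1.3 the event is bad, and a hazard ratio below 1 is a benefit. For 9.3.1.4 the event is leaving hospital, and a hazard ratio below 1 means a lower discharge rate, that is, a longer stay. A criterion carried over unchanged labels the results backwards. SAP 9.3.1.5 adds to the exposure: it extends the subgroup analyses by ACLF grade and region to these endpoints and reports hazard ratios with confidence intervals but no p-values. Discharge hazard ratios would then be tabulated beside death hazard ratios with nothing to say that benefit lies on the other side of 1.

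**Absolute estimates.** A subject who dies in hospital will never be discharged. Censoring at death makes the Kaplan-Meier estimate behave as if that subject could still leave later at the same rate as those who remain. One minus Kaplan-Meier is then higher than the proportion actually discharged. The design assumes about 50% mortality by Day 90 in the control group, so the gap may not be small.

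**Working it through.** **1. Direction, from the text.**

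| Section | Event | Meaning of HR (PE-A/SMT) below 1 |
|---|---|---|
| 9.3.1.1 | death in hospital | fewer deaths: favourable |
| 9.3.1.2, 9.3.1.3 | transplant or death | fewer events: favourable |
| 9.3.1.4 | discharge | slower discharge: unfavourable |

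SAP 6.5, 9.3.1.4 and 12 neither reverse the direction nor exempt discharge. The criterion reaches this endpoint only through the 9.3.1 cross-reference, because Protocol 9.1.2.4 has none.

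**2. What the literal criterion would do.** Cox models were fitted to 1,000 simulated trials per scenario, with 190 subjects per arm, exponential discharge times, death censored with a median of 90 days in both arms, and follow-up to Day 90. The discharge medians are assumptions.

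| Median days, PE-A vs SMT | Mean HR | p at most 0.05 and HR below 1 | p at most 0.05 and HR above 1 |
|---|---|---|---|
| 14 vs 21 (faster with PE-A) | 1.50 | 0% | 94.6% |
| 21 vs 14 (slower with PE-A) | 0.67 | 95.6% | 0% |
| 18 vs 18 | 1.00 | 2.1% | 2.9% |

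This shows which way the criterion points. It is not evidence that anyone would apply it in that way.

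**3. Death hazards for the illustration.** The plan gives no figure for discharge. The death hazards come from its sample-size section (SAP 6.2, Protocol 9.2):
- SMT: −ln(0.50)/90 = 0.0077 per day, as stated there.
- PE-A: −ln(0.65)/90 = 0.0048 per day.
- Ratio: ln(0.65)/ln(0.50) = 0.6215, as stated there.

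**4. Size of the overstatement at Day 90.** Let g be the discharge hazard, assumed equal in both arms, and h the death hazard. Transplant is ignored.
- Kaplan-Meier with deaths censored: 1 − exp(−90g).
- Proportion actually discharged (cumulative incidence): g/(g+h) × [1 − exp(−90(g+h))].

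Worked case, g = 0.03:
- Kaplan-Meier: 1 − exp(−2.7) = 93.3%.
- SMT: (0.03/0.0377) × [1 − exp(−3.393)] = 0.796 × 0.966 = 76.9%.
- PE-A: (0.03/0.0348) × [1 − exp(−3.132)] = 0.862 × 0.956 = 82.4%.

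| g per day | Kaplan-Meier, both arms | Actual, SMT | Actual, PE-A | Overstatement, SMT | Overstatement, PE-A |
|---|---|---|---|---|---|
| 0.02 | 83.5% | 66.2% | 72.0% | 17.2 points | 11.5 points |
| 0.03 | 93.3% | 76.9% | 82.4% | 16.4 points | 10.8 points |
| 0.05 | 98.9% | 86.2% | 90.6% | 12.7 points | 8.3 points |

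The range is therefore about 8 to 17 points.

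**5. Day 28 and the quartiles.** Putting 28 for 90 at g = 0.03 gives Kaplan-Meier 56.8% against 51.9% (SMT) and 53.7% (PE-A), a gap of 3 to 5 points. The Kaplan-Meier 75th percentile is ln(4)/0.03 = 46 days. In the SMT arm, 75% are actually discharged only at −ln(1 − 0.75 × 0.0377/0.03)/0.0377 = 76 days.

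**The case against.** The strongest reply is that the superiority sentence belongs to the primary endpoint. Section 9.1.2 introduces it with the survival objective and with hypotheses about the hazard of death, and its wording is about deaths and survival throughout. Methodology in 9.3.1 would then naturally mean the stratified Cox, Kaplan-Meier and log-rank methods, adapted to each event. SAP 6.5 confines multiplicity-controlled testing to the primary and two ordered secondary endpoints, and section 12 announces no new criterion for discharge. This carries weight. A reader might infer that the trial will declare slower discharge superior, and the documents do not support that: no formal superiority conclusion on discharge is planned, and an estimate of 1.4 would be reported as 1.4 with the same interval and p-value. What remains is that the SAP never limits the cross-reference, although it states exceptions elsewhere, for example the stratification and p-value rules in 9.3.1.5.

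On censoring, a reader might infer that the comparison between arms is invalid, or that equal curves hide a treatment benefit. Neither follows. Censoring at death gives a legitimate cause-specific comparison of discharge rates. In the illustration those rates are equal by assumption, so a hazard ratio of 1 is the right answer to that question. The 4 to 6 more subjects per 100 who leave hospital alive reflect lower mortality, which the primary endpoint and in-hospital death already measure. Only the absolute Kaplan-Meier quantities are at fault.

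The illustration is also open to challenge. The discharge hazards are not in the documents, transplant is left out, and constant death hazards do not match Protocol Table 2-2, where mortality for the three eligible grades at diagnosis is already 34% at Day 28 against 46% at Day 90. The figures show scale and do not forecast this trial.

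**Conclusion.** The point holds in a limited form. Read literally, the inherited criterion is reversed for time to discharge, and nothing in the SAP corrects it. The consequence is a wrong label on an exploratory result. It does not change a number, a confirmatory claim or the sample size.

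The second part does affect reported numbers. With in-hospital deaths and transplants censored, the Kaplan-Meier probabilities overstate discharge and the quartiles come too early. That direction follows from the censoring rule whenever such events occur. The size of about 8 to 17 percentage points at Day 90 rests on assumed discharge hazards of 0.02 to 0.05 per day, equal in both arms, constant design death hazards and no transplants. Both parts are worth correcting because the remedy is specific and cheap.

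**What to change.** In SAP 9.3.1.4:
- State that a hazard ratio above 1 favours SMT+PE-A 5% and that the hazard-ratio-below-1 superiority criterion of 9.1.2 does not apply to this endpoint. Put the same note on the subgroup outputs under 9.3.1.5.
- Keep the stratified Cox and log-rank comparison, and describe it as cause-specific, with death and transplant censored.
- Report cumulative incidence of discharge by arm at Days 28 and 90, with death and transplant as competing events, in place of or beside the Kaplan-Meier probabilities and quartiles.

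Record the change in SAP section 12, since Kaplan-Meier is the protocol's method for this endpoint.

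Keeping subjects who die in the risk set to Day 90 as never discharged is not proposed. It would change the question by mixing mortality with speed of discharge.

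The cost is a few sentences and one extra program, with no new data. The small downside is a documented departure from the protocol's method in an open-label trial after its last patient visit (14 April 2025, SAP section 2). It should therefore be presented as a clarification and an added description.
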